6.2.1. Enrollment Visit

For the patients who participated in a SJM-sponsored regulatory or first-in-human trial, the enrollment will occur retrospectively (after the date they received their Portico Valve). The historical data collected through 1 year in those trials will not need to be re-collected for this clinical investigation.

For patients indicated for implantation of a new Portico Valve, the enrollment will occur prospectively (before the date they will receive their Portico Valve) at a maximum of 45 days prior to the date of the Portico Valve implant and no later than the date of the Portico Valve implant but before the implant takes place.

The following enrollment activities are performed after the patient has been screened and must occur before any investigational procedure/visit.

- The principal or delegated site personnel is responsible for screening all potential patients to determine patient eligibility for the investigation
- If a patient meets all pre-procedural inclusion criteria and does not meet any of the pre-procedural exclusion criteria, he/she is eligible for the investigation.
 - Inform the eligible patient verbally about the investigation and provide the information sheet and consent to the patient.
 - Provide ample time for the patient to read and understand the information sheet and consent and to consider participation in the clinical investigation. Invite the patient to ask questions if needed.
 - Obtain the signature and date hand-written from the eligible patient on the EC approved informed consent (If an eligible patient does not sign and date the informed consent, he cannot participate in the investigation. No further protocol required activities are performed)
 - Obtain the signature and date from the principal or delegated investigator who obtained consent on the EC approved consent
 - Provide one copy of the signed and dated version of the informed consent to the patient (signed by both patient and investigator)
 - File the original signed and dated version of the informed consent in the Investigator Site Binder (ISB).
- Record enrollment information (name of the investigation, date of consent and Inclusion/exclusion information) in the hospital records and complete the Enrollment form preferably within 5 days after enrollment (failure to meet this timeline will not be considered a protocol deviation)
- Notify the sponsor by submitting the enrollment form.

NOTE: As soon as the patient signs the PIC, adverse events and device deficiencies need to be reported according to the guidelines mentioned in section 7.3. For Cohort B, patients, adverse event and device deficiency reporting includes events having occurred after their last documented follow-up visit.

In case the patient was consented to participate in the investigation, but does not meet inclusion/exclusion criteria (i.e. screen failure before the index procedure), the following actions shall be taken:

- Document enrollment information (consent and inclusion/exclusion) in the hospital records; complete the Enrollment, deviation and Termination forms. The form must be authorized / approved by the principal or delegated investigator.
 - Refer to Appendix C: Data Collection Method.
 - Inform the patient about his/her withdrawal.

- The EC/IRB and NCA/NRA should be notified appropriately about any deviations with regards to obtaining the informed consent.

6.2.2. Baseline Visit (Cohort A only)

This visit can take place the same day as the enrollment visit. The data from previously conducted diagnostic tests/procedures, as indicated with an “ (X) as applicable

, performed as standard of care will be collected during this visit. It is not necessary to repeat these tests if they were collected within the clinical investigation visit window. All other data must be collected after obtaining clinical investigation specific consent and within 45 days prior to the TAVI procedure. The baseline visit consists of the following activities:

- Demographics
- Medical and Cardiovascular History
- Native aortic valve assessment
- Access site assessment (Trans-femoral, trans-apical, etc.)
- Surgical Risk Assessment
- Frailty Assessment (including assessment of 5 meters walking time, grip strength, wasting and malnutrition and cognitive impairment or dementia via MMSE)
- Blood sample (Serum Albumin value as part of frailty assessment. Creatinine, Hemoglobin if available (SOC) and Troponin values)
- Physical Assessment
- 12 lead ECG
- Medication assessment
- Echocardiogram
- NYHA Classification
- QoL questionnaire (EQ-5D)
- 6MWT
- Modified Rankin Scale
- Adverse events assessment
- Device Deficiency assessment

6.2.3. Portico Valve Implant visit - Index procedure (Cohort A only)

The medical team performing the TAVI procedure will typically consist of:

- An interventional cardiologist or a cardiac surgeon at the site will perform the procedure according to local guidelines.
- A second operator (a cardiac surgeon or a cardiologist) may be present during the procedure as needed.
- An anesthesiologist and/or a perfusionist as needed.

The implanting physician should be trained according to SJM Portico training program prior to implant of the Portico Valve.

NOTE: The above medical team members do not need to be trained on the protocol if they only perform the Portico Valve implant and no other study related tasks.

NOTE: Anticoagulation is left to the physician’s discretion” or should be established as with any other biological valve implantation, considering risks and benefits for the patient.

At least one device may be deployed in every patient who has signed the PIC and is not procedurally excluded. Although not recommended, if a physician determines it is in the best interest of the patient to have a second device placed, a patient may receive an additional device.

The procedure visit will consist of the following steps:

- Pre-implant (access preparation)
- Implant (valve deployment)
- Aortic regurgitation assessment combining angiography, echocardiography and hemodynamic approach
- Implant depth and prosthesis-patient mismatch assessment
- Post-implant (access closure)
- Medication assessment
- Device implantability assessment
- Adverse events assessment
- Device Deficiency assessment
- Resource utilization assessment

It is strongly recommended to follow the peri-procedural instructions for the assessment of aortic regurgitation and implant depth as mentioned in Appendix I. However, failure to follow these instructions will not be considered a protocol deviation.

Procedural Exclusion

During the procedure, the implanting physician may determine the implantation of the Portico Valve is either not feasible or not in the best interest of the patient. Reasons for procedural exclusion may include, but are not limited to, anatomy that is not suitable for implantation, inability to gain access, ventricular arrhythmia, or any other contraindication. Any patient that does not have a delivery system enter his or her body will be considered “procedurally excluded.”

Data will be collected on these subjects from the Baseline through the 30-day follow-up, including reason for exclusion and collection of possible adverse events.

The patient should then be withdrawn from the clinical investigation.

Following the procedure, the delivery and loading systems should be securely disposed as per hospital requirements for hazardous materials. If there are any concerns noted with the delivery system, loading system, or valve during the procedure, they should be returned to SJM per instructions provided in Appendix K: Explant, Return, and Analysis of Valve and Appendix L: Instructions for device return - Large and Small Kits.

6.2.4. Pre-Discharge visit (Cohort A only)

The pre-discharge visit will take place at the time of hospital discharge or within seven days after the index procedure, whichever occurs first. If the patient is expected to be discharged over the weekend, the discharge tests may be completed on the last week day prior to discharge. The assessment will include:

- Physical assessment
- Blood sample (between day 2 to 4 Post-implant or at discharge whatever occurs first) to obtain Hemoglobin, Creatinine and Troponin values
- 12 lead ECG (within 24hrs Post-implant and at hospital discharge but no later than 7 days Post-implant, whatever occurs first).
- Medication assessment
- Echocardiography (if a post-procedure echo has been done within 24 hours prior to discharge, an additional discharge echo is not required)
- NYHA functional classification
- QoL questionnaire (EQ-5D)
- Modified Rankin Scale
- Adverse events assessment
- Device Deficiency assessment
- Resource utilization assessment

6.2.5. 30 Day follow-up visit (Cohort A only)

The 30 Day visit will take place at 30days (-7 days, +14days) after the index procedure, and will include:

- Frailty Assessment by means of the following components: 5 meters walking time, grip strength, wasting and malnutrition (including blood sample to obtain Serum Albumin value) and cognitive impairment or dementia (via MMSE)
- Physical assessment
- 12 lead ECG
- Medication assessment
- Echocardiography
- NYHA functional classification
- QoL questionnaire (EQ-5D)

- 6MWT
- Modified Rankin Scale
- Adverse events assessment
- Device Deficiency assessment
- Permanent Pacemaker Control (if applicable)
- Resource utilization assessment

6.2.6. 1 Year follow-up visit (Cohort A only)

The 1 Year visit will take place at 365 days (\pm 90days) after the index procedure, and will include:

- Frailty Assessment by means of the following components: 5 meters walking time, grip strength, wasting and malnutrition (including blood sample to obtain Serum Albumin value) and cognitive impairment or dementia (via MMSE)
- Physical assessment
- 12 lead ECG
- Medication assessment
- Echocardiography
- NYHA functional classification
- QoL questionnaire (EQ-5D)
- 6MWT
- Modified Rankin Scale
- Adverse events assessment
- Device Deficiency assessment
- Resource utilization assessment

6.2.7. 2 Year follow-up visit

To accommodate subject referrals from distant hospitals, the referring physician may conduct the 2 Y follow-up visit. In such cases, the investigator may contact the referring physician's office and/or obtain the appropriate source documents to complete Case Report Forms (CRFs).

The 2 Year visit will take place at 730 days (\pm 90 days) after the index procedure, and will include:

- Physical assessment
- Medication assessment
- Echocardiography

- NYHA functional classification
- 6MWT
- Adverse events assessment
- Device Deficiency assessment

6.2.8. 3 Year follow-up visit

To accommodate subject referrals from distant hospitals, the referring physician may conduct the 3 Y follow-up visit. In such cases, the investigator may contact the referring physician's office and/or obtain the appropriate source documents to complete Case Report Forms (CRFs).

The 3 Year visit will take place at 1095days (\pm 90days) after the index procedure, and will include:

- Physical assessment
- Medication assessment
- Echocardiography
- NYHA functional classification
- 6MWT
- Adverse events assessment
- Device Deficiency assessment

6.2.9. 4 Year follow-up visit

To accommodate subject referrals from distant hospitals, the referring physician may conduct the 4 Y follow-up visit. In such cases, the investigator may contact the referring physician's office and/or obtain the appropriate source documents to complete Case Report Forms (CRFs).

The 4 Year visit will take place at 1460days (\pm 90days) after the index procedure, and will include:

- Physical assessment
- Medication assessment
- Echocardiography
- NYHA functional classification
- 6MWT
- Adverse events assessment
- Device Deficiency assessment

6.2.10. 5 Year follow-up visit

To accommodate subject referrals from distant hospitals, the referring physician may conduct the 5 Y follow-up visit. In such cases, the investigator may contact the referring physician's office and/or obtain the appropriate source documents to complete Case Report Forms (CRFs).

The 5 Year visit will take place at 1825days (\pm 90days) after the index procedure, and will include:

- Physical assessment
- Medication assessment
- Echocardiography
- NYHA functional classification
- 6MWT
- Adverse events assessment
- Device Deficiency assessment

6.2.11. Unscheduled Visit

An unscheduled visit is defined as a visit that occurs between two scheduled investigational visits where the patient is examined for either a physician requested follow-up or for an adverse event. Any data collected related to the clinical investigation endpoints needs to be documented such as Echocardiography, ECG or modified Rankin Stroke Scale by completing the appropriate section of the Follow-up or Echocardiogram electronic Case Report Form (eCRF).

NOTE: The Modified Rankin scale should be completed at every visit and additionally (if possible) 90 days after any neurological event (stroke, TIA, encephalopathy). Use the unscheduled visit to record the Modified Rankin scale score. This score can be obtained over a telephonic interview. Failure to obtain the Modified Rankin scale score 90 days after the onset of a neurological event will not be considered a protocol deviation.

NOTE: For cohort B patients, in the event of an unscheduled visit occurring after the patient 1 year follow-up, this visit is to be documented as part of this clinical investigation.

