5.3.2 Secondary Endpoints

- Evaluation of the VARC-2¹⁹ defined event rates at 30 days, 1 year and annually through 5 years post implant. Definitions are detailed in Appendix D: VARC 2 Endpoints Definitions.
 - All-Cause Mortality
 - Cardiovascular Mortality
 - Myocardial Infarction
 - Stroke (disabling and non-disabling)
 - New or worsened conduction disturbances and cardiac arrhythmias (including pacemaker implantation rate at 30 days and new-onset atrial fibrillation (AF))
- Evaluation of the VARC-2¹⁹ defined event rates at 30 days from the index procedure.
 - Vascular access site complication (major and minor)
 - Bleeding (life-threatening, major and minor)
 - Acute kidney injury

- Prosthetic valve function at 30 days, 1 year and annually through 5 years post implant. (Includes prosthetic valve stenosis and prosthetic valve regurgitation).
- Clinical benefit endpoints at 30 days, 1 year and annually through 5 years post implant (if available)
 - NYHA functional classification
 - 6 Minute Walk Test (6MWT)
 - Quality of life measured with EQ-5D questionnaire through 1 year post-implant
- Evaluation of the TAVI-related resource utilization through hospital discharge (e.g. index procedural hospital/physician resources)
- Interim reporting at 30 days and 1-year all-cause mortality data may be performed on a subset of patients and compared with an appropriate external comparator. The results will be presented to appropriate agencies in France and in other countries where it will be deemed necessary for reimbursement purposes.

NOTE: Should new VARC or ESC Guidelines be published, endpoint analysis would be adjusted accordingly and analyzed to the extent that the previously gathered data supports the analyses based on the most current guidelines.

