	
Echocardiograms can be requested to be sent to an echo Core Laboratory. If requested, exams should be recorded in Dicom format and should be de-identified prior to sending. Routine echocardiograms can be used to complete the echocardiogram study Case Report Forms (CRFs).

NYHA Classification (From 2Y visit onward for Cohort B)
	
The New York Heart Association (NYHA) Functional Classification provides a simple way of classifying the extent of heart failure.

QoL questionnaire (EQ-5D) (NAP for Cohort B)
	
The EQ-5D questionnaire will be used. It is a standardized instrument for use as a measure of health outcomes.

The six-minute walking test (From 2Y visit onward for Cohort B)
	
The six-minute walking test (6MWT) is a commonly used objective measure of functional exercise capacity in individuals with moderately severe impairment. For further details/instructions, please refer to Appendix G: ATS Guidelines²⁵ for the Six Minute Walk Test instructions.

Modified Rankin scale (mRS)
	
The modified Rankin Scale (mRS) is a functional measurement to assess the degree of disability or dependence in the daily activities of people who have suffered a stroke. mRS at Enrollment/Baseline, 30days, 1year and is to be completed additionally (if possible) 90days after any neurological event (stroke, TIA, encephalopathy) This assessment must be completed by a rater who has a current certificate that demonstrates completion of an accredited training program for this stroke scale, using the structured interview found in Appendix H: Structured Interview for the Modified Rankin Scale (mRS).

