
Stroke and TIA (VARC 2)
	
Diagnostic criteria
 
 • Acute episode of a focal or global neurological deficit with at least one of the following: change in level of consciousness, hemiplegia, hemiparesis, numbness or sensory loss affecting one side of the body, dysphasia or aphasia, haemianopia, amaurosis fugax, or other neurological signs or symptoms consistent with stroke. • Stroke: duration of a focal or global neurological deficit ≥ 24h; OR < 24h, if available neuroimaging documents a new hemorrhage or infarct; OR the neurological deficit results in death. • TIA: duration of a focal or global neurological deficit < 24h, any variable neuroimaging does not demonstrate a new hemorrhage or infarct. • No other readily identifiable non-stroke cause for the clinical presentation (e.g. brain tumor, trauma, infection, hypoglycaemia, peripheral lesion, pharmacological influences) to be determined by or in conjunction with the designated neurologist^a. • Confirmation of the diagnosis by at least one of the following: 
 ○ Neurologist or neurosurgical specialist ○ Neuroimaging procedure (CT scan or brain MRI), but stroke may be diagnosed on clinical grounds alone. 
Stroke classification
 
 • Ischaemic: an acute episode of focal cerebral, spinal, or retinal dysfunction caused by infarction of the central nervous system tissue. • Haemorrhagic: an acute episode of focal or global cerebral or spinal dysfunction caused by intraparenchymal, intraventricular, or subarachnoid haemorrhage. • A stroke may be classified as undetermined if there is insufficient information to allow categorization as ischaemic or haemorrhagic. 
Stroke definitions^b
 
 • Disabling stroke: an mRS score of 2 or more at 90 days and an increase in at least one mRS category from an individual's pre-stroke baseline. • Non-disabling stroke: an mRS score of < 2 at 90 days or one that does not result in an increase in at least one mRS category from an individual's pre-stroke baseline 
^a Patients with non-focal global encephalopathy will not be reported as a stroke without unequivocal evidence based upon neuroimaging studies (CT scan or Brain MRI)
 
^bModified Rankin Score assessments should be made by qualified individuals according to a certification process.

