Appendix H: Structured Interview for the Modified Rankin Scale (mRS)

The modified Rankin Scale (mRS) score is to be determined and graded by a certified rater.

The determination of the scale should be made from 5 to 0, i.e., the order presented.

The purpose of the mRS is to record whether the patient is dead, severely, moderately, or slightly disabled and if not dead or disabled, whether the patient is performing all usual activities without symptoms or not.

Because patients and family members may understate the severity of disability, it is important for the rating clinician to understand that the mRS is a clinical scale and not a patient-reported outcome. The rater may ask questions but must assess the disability whether or not in agreement with the patient or family (26).

5: Severe disability; someone needs to be available at all times; care may be provided by either a trained or an untrained caregiver.

Question: Does the person require constant care?

4: Moderately severe disability; need for assistance with some basic activities of daily living (ADL), but not requiring constant care.

Question: Is assistance essential for eating, using the toilet, daily hygiene, or walking?

3: Moderate disability; need for assistance with some instrumental ADL but not basic ADL.

Question: Is assistance essential for preparing a simple meal, doing household chores, looking after money, shopping, or traveling locally?

2: Slight disability; limitations in participation in usual social roles, but independent for ADL.

Questions: Has there been a change in the person's ability to work or look after others if these were roles before stroke? Has there been a change in the person's ability to participate in previous social and leisure activities? Has the person had problems with relationships or become isolated?

1: No significant disability; symptoms present but no other limitations.

Question: Does the person have difficulty reading or writing, difficulty speaking or finding the right word, problems with balance or coordination, visual problems, numbness (face, arms, legs, hands, feet), loss of movement (face, arms, legs, hands, feet), difficulty with swallowing, or other symptom resulting from stroke?

0: No symptoms at all; no limitations and no symptoms.

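### Disabling stroke is defined by a 90-day mRS that sites need not collect, so fatal and unscored strokes cannot be classified from the text supplied

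*Combined protocol and SAP*

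**What the plan says.** Section 5.3.2 makes stroke, split into disabling and non-disabling, one of the VARC-2 "defined event rates at 30 days, 1 year and annually through 5 years post implant".

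Appendix D gives the split. The first class is "Disabling stroke: an mRS score of 2 or more at 90 days and an increase in at least one mRS category" from the patient's pre-stroke level. The second is a 90-day score below 2, "or one that does not result in an increase in at least one mRS category". Appendix D also counts as a stroke a neurological deficit that ends in death.

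The 90-day score is conditional wherever it is requested. Table 3 in Section 6.2 reads "mRS at Enrollment/Baseline, 30days, 1year and is to be completed additionally (if possible) 90days after any neurological event", and footnote e of Table 2 carries the same qualifier. Section 6.2.11 allows the score to be taken by telephone and then states: "Failure to obtain the Modified Rankin scale score 90 days after the onset of a neurological event will not be considered a protocol deviation".

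Appendix H describes the mRS as recording, among other states, whether the patient has died, but the grades run only over the living: "The determination of the scale should be made from 5 to 0, i.e., the order presented".

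Routine timing is inconsistent. Section 6.2.11 says "The Modified Rankin scale should be completed at every visit". Table 2 schedules the mRS at baseline, pre-discharge, 30 days and 1 year only, and the visit lists for years 2 to 5 omit it. Table 3 also leaves out pre-discharge, which Section 6.2.4 includes.

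**The concern.** The endpoint split rests on a single measurement, and a site can follow the protocol fully without taking it. The measurement is least likely to exist in the patients who matter most to the split: those who die before day 90, and those too disabled to attend or to be interviewed. Unless a stroke with no score is put in the disabling class, every disabling stroke that goes unscored lowers the reported disabling-stroke rate. The gap would then vary with how well sites follow up neurological events rather than with the device. An adjudication committee can review the records, but it cannot create a 90-day score that nobody took.

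**Working it through.** The documents give no stroke rate and no expected share of missing scores, so there is no planned figure to reproduce. The check has two parts: the text, and an illustration under stated assumptions.

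**1. Can a scheduled visit supply the 90-day score?**

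Inputs (Table 2 and the visit descriptions in Section 6.2): the 30-day visit has a window of -7 to +14 days, and the 1-year visit is at 365 ± 90 days.

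- The 30-day window closes at day 30 + 14 = 44.
- The 1-year window runs from day 365 − 90 = 275 to day 365 + 90 = 455.
- A stroke on day d has its 90-day point on day d + 90. For d = 0 to 30 this is day 90 to 120, where no visit is scheduled.
- The 90-day point falls before the 1-year window for every stroke up to day 184 (184 + 90 = 274).
- For strokes from day 185 to 365 the 90-day point lies between days 275 and 455. The 1-year visit could coincide with it, but only by chance.
- After 1 year, Table 2 schedules no mRS, so the split depends wholly on the conditional score.

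**2. Which strokes can be classified from Appendices D and H?**

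| Situation at day 90 | Disabling? | Non-disabling? |
|---|---|---|
| Alive, scored | Decided by the definition | Decided by the definition |
| Alive, not scored | Cannot be judged | Cannot be judged |
| Died of the stroke before day 90 | No numeric grade, so a score of 2 or more cannot be shown | No score below 2; no measured absence of change |

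Section 9.4 gives no rule for the last two rows. It leaves other secondary analyses to a separate statistical analysis plan. Section 14.3.2 sends adjudication to a committee working under VARC-2 and a charter. Neither that plan nor the charter is in the file.

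**3. How far could the rate move? (illustration)**

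Assumptions: stroke rate r = 5% (3% and 8% also checked); share of strokes without a 90-day score m = 10% to 40%; half of the scored strokes disabling; N = 866, the Cohort A minimum in Section 9.2.1.

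- Best case (no unscored stroke is disabling): 0.5 × r × (1 − m)
- Worst case (all unscored strokes are disabling): 0.5 × r × (1 − m) + r × m = 0.5 × r × (1 + m)
- Ratio: (1 + m)/(1 − m), which does not depend on r or N

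At r = 5%, 866 × 0.05 = 43.3 strokes:

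| m | Unscored strokes | Best case | Worst case | Ratio |
|---|---|---|---|---|
| 10% | 4.3 | 2.25% | 2.75% | 1.22 |
| 20% | 8.7 | 2.00% | 3.00% | 1.50 |
| 40% | 17.3 | 1.50% | 3.50% | 2.33 |

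The ratios are the same at stroke rates of 3% and 8%.

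**The case against.** The strongest reply is that the governing rules may sit elsewhere. Events are adjudicated under the committee's charter, and a separate analysis plan is announced; either may say how fatal and unscored strokes are classed. This stands, and it limits the claim to the text supplied.

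The committee would also have other evidence. Strokes that are serious adverse events must be reported within 3 calendar days, endpoint data from unscheduled visits must be recorded, and a patient who has a stroke in the first year and reaches the 1-year visit has a later mRS. That can inform a judgement, but it is not the 90-day value that Appendix D requires, and it does not help with early deaths.

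A reader might infer that fatal strokes will be counted as non-disabling, because death records no rise in score. The documents do not support this. No section sets such a default, a dead patient does not have a score below 2, and an absent score is not a measured absence of change. Nor is it right to say that the scale ignores death: Appendix H names death as something the scale records and omits only a number for it.

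A reader might also infer that strokes in years 2 to 5 must be compared with a score up to 4 years old. Appendix D refers to the individual's pre-stroke level, not the last scheduled score, and the Appendix H interview asks about roles and activities before the stroke, so the reference can be obtained at the time.

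Finally, the reach is narrow. The study has one arm, no hypothesis test is planned on this endpoint, and deaths from neurological events are already captured as cardiovascular deaths. That stands and holds the severity down. Calling a missed score a deviation does not itself produce a score, but it removes an explicit permission to skip the measurement that defines the endpoint.

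**Conclusion.** The concern holds in a limited form. Under the text supplied, strokes that are fatal before day 90 or have no 90-day score cannot be classified, and the protocol expressly tolerates the missing score. Missing scores are plausibly concentrated in the most severe strokes, so the disabling-stroke rate is likely understated. That direction is a reasoned expectation; the documents hold no data on it.

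The size rests wholly on assumptions. With 10% to 40% of strokes unscored and half of the scored strokes disabling, the worst-case to best-case ratio is about 1.2 to 2.3. A reader might take the possible swing to be as large as the disabling-stroke rate itself. It is smaller: the swing is r × m, and if half of all strokes are disabling (r/2) it is 2m of that rate, or 20%, 40% and 80% at m = 10%, 20% and 40%. These are also all-or-none bounds, so the real effect would lie inside them.

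The all-stroke count, the primary endpoint of all-cause mortality and the sample size are not affected. This is a cheap improvement to a descriptive secondary endpoint that the plan should make.

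**What to change.** 1. In Tables 2 and 3 and Section 6.2.11, remove the feasibility qualifier on the 90-day mRS for strokes, and delete the sentence that excuses a missing score. Require the score for every surviving patient with a stroke, by telephone if needed, from a certified rater as Table 3 already demands.
2. In Appendix D, state that fatal strokes are reported either as disabling or as a separate fatal class. If the committee's charter already has a rule, cite it there.
3. In Section 9.4 or the separate analysis plan, report strokes without a 90-day score as unclassified, give their number, and show the disabling-stroke rate with best-case and worst-case bounds.
4. Reconcile Section 6.2.11, which asks for the mRS at every visit, with Tables 2 and 3, and Table 3 with Table 2 and Section 6.2.4 on the pre-discharge score.

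The cost is wording in a few places, one call by a certified rater for each surviving stroke patient not seen at 90 days, and a few more recorded deviations.
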